5.6 Premature Termination of the Study

The clinical study may be terminated prematurely or suspended at the request of Health Authorities or if new safety or efficacy information leads to an unfavorable risk benefit judgment for berzosertib. The Sponsor may discontinue the study if it becomes unjustifiable for medical or ethical reasons or because of discontinuation of clinical development of berzosertib. In case of termination of the study, the Health Authorities and Independent Ethics Committees (IECs)/Institutional Review Boards (IRBs) will be informed about the discontinuation of the study in accordance with applicable regulations.

5.7 Definition of End of Study

This rollover study will be ongoing while any participant is receiving berzosertib. The end of the study will be the day when the last participant has completed the Safety Follow Up visit to be scheduled 28 (+7) days after the last administration of berzosertib.

The Sponsor may terminate the study at any time once access to berzosertib for participants still benefiting is provisioned via expanded access, marketed product or another mechanism of access as appropriate.

6 Study Intervention

Study intervention is any investigational intervention(s), marketed product(s), placebo, or medical device(s) intended to be administered to a study participant per the study protocol.

6.1 Description of Study Intervention

Study intervention dosing and schedule for participants in this rollover study will be identical to the dosing and schedule of the study intervention(s) received in the study from which the participant transitioned. This implies that participants receiving combinations of berzosertib with any other drugs in the study from which the participant is transitioned will continue to receive the same study interventions in this Safety Follow Up study.

The study intervention (berzosertib) administered in this study will be supplied and distributed by the Sponsor or designee. Combination drugs will be obtained from the local pharmacies.

6.2 Dosage and Administration

Dosage and schedule of berzosertib administration will depend on the details of treatment in the VX13-970-002 study from which the participant transitioned.

More general recommendations for study intervention administration and management (e.g., details of administration, dose modification for toxicity, missed doses etc.) are given in the

Document No. CC	C O N F I D E N T I A L I N F O R M A T I O N	17/54	
	Global Version ID: CCI		

VX13-970-002 protocol from which the participants are transitioning. Details of dose preparation are provided in the Formulation Preparation Instructions (see Appendix III).

The dose of berzosertib will be infused intravenously over 60 minutes (\pm 10 minutes). If the total volume of the infusion exceeds 600 mL, the infusion time may be extended beyond 60 minutes, as tolerated, but no more than 90 minutes. Details of dose preparation for berzosertib will be provided in the Pharmacy Manual.

Intravenous administration of berzosertib is independent of food intake.

To minimize the possibility of phlebitis, berzosertib should be administered through a large bore catheter into a large caliber peripheral vein. If any participant develops phlebitis or signs or symptoms of inflammation that may progress to phlebitis or that the participant cannot tolerate, standard measures should be employed to ameliorate these symptoms (including removal of the infusion catheter and resumption of infusion through a different vein).

6.3 Assignment to Treatment Groups

Participants on active treatment will continue receiving treatment at the same dosage and frequency as in the study the participant transitioned from.

6.4 Concomitant Medications and Therapies

All concomitant medications taken by the participant during the study, from the date of signature of informed consent are to be recorded in the appropriate section of the electronic Case Report Form (eCRF), noting the name, dose, duration and indication of each drug. Nondrug interventions and any changes to a concomitant medication or other intervention should also be recorded in the eCRF.

6.4.1 Permitted Medicines

Any medications that are considered necessary to protect participant welfare and will not interfere with the study intervention may be given at the Investigator's discretion.

Premedication with hydrocortisone and chlorphenamine and rescue medications may be administered to address anticipated adverse reactions or anticipated emergency situations (see Section 6.4.5).

Antiemetics and supportive therapies will be administered or dispensed to participants according to individual site Standard of Care.

6.4.2 Prohibited Medicines

In vitro drug metabolism studies suggest that berzosertib is a substrate of cytochrome P450 (CYP) 3A, and its systemic exposure may be affected by concomitant medications that are strong CYP3A inhibitors or inducers.

Document No. CCI	C O N F I D E N T I A L I N F O R M A T I O N	18/54	
	Global Version ID: CC		

Prior and concomitant medication restrictions during treatment include:

- Grapefruit/grapefruit juice, Seville or blood oranges/marmalade
- Strong CYP3A inhibitors or inducers
- Ototoxic or Nephrotoxic medication for participants receiving carboplatin.

For a more complete list of study prohibited and cautioned medication/food/activity, see Appendix IV.

6.4.3 Other Interventions

Not applicable.

6.4.4 Special Precautions

6.4.4.1 Risk of Phototoxicity

All participants should be advised to avoid prolonged or intense sun exposure, sunlamps, and tanning beds. Use of sunscreen, clothing, and eyewear that decrease sun exposure is recommended.

6.4.4.2 Contraception

Women of childbearing potential and males must use a highly effective method of contraception (i.e., methods with a failure rate of less than 1% per year when used consistently and correctly) as detailed below throughout the study and for 6 months after the last dose of assigned treatment.

All participants must undergo appropriate contraceptive counselling. The Investigator or any skilled representative of the study site should counsel participants on the most effective method(s) for avoiding pregnancy during the study.

Men

Acceptable contraceptive methods must be used from Screening visit through 6 months after last dose of the study intervention, and include the following:

- True abstinence (abstinence of any sexual intercourse, when in line with the preferred and usual lifestyle of the participant). Periodic abstinence (e.g., calendar, symptothermal, postovulation methods) and withdrawal are not acceptable methods of contraception.
- Condom with or without spermicide. In addition, the female partner must use a highly effective contraception method as outlined in Appendix I.
- Surgical sterilisation (vasectomy) with a negative sperm post-vasectomy semen analysis; If the absence of sperm has not been confirmed, men must use a condom and their female partner must use a highly effective contraception method as outlined in Appendix I.

Men must not donate sperm from Screening visit through 6 months after last dose of the study intervention.

Document No. CC	C O N F I D E N T I A L I N F O R M A T I O N	19/54	
	Global Version ID: CCI		

Women of Nonchildbearing Potential

Women in the following categories are not considered women of childbearing potential:

- 1. Premenopausal female with 1 of the following:
 - Documented hysterectomy
 - Documented bilateral salpingectomy
 - Documented bilateral oophorectomy

Note: Documentation can come from the site personnel's: review of participant's medical records, medical examination, or medical history interview.

- 2. Premenarchal
- 3. Postmenopausal female
 - Females who are postmenopausal (age-related amenorrhea ≥ 12 consecutive months and increased follicle-stimulating hormone (FSH) > 40 mIU/mL), or who have undergone hysterectomy or bilateral oophorectomy are exempt from pregnancy testing. If necessary to confirm postmenopausal status, a follicle-stimulating hormone will be drawn at Screening.
 - Females on hormone replacement therapy (HRT) and whose menopausal status is in doubt will be required to use one of the non-hormonal highly effective contraception methods if they wish to continue their hormone replacement therapy during the study. Otherwise, they must discontinue hormone replacement therapy to allow confirmation of postmenopausal status before study enrollment.

All other female participants (including participants with tubal ligations and participants who do not have a documented hysterectomy) will be considered to be of childbearing potential.

Women of Childbearing Potential

A highly effective contraception as outlined in Appendix I must be used before start of first dose of study treatment, during the treatment period and for at least 6 months after the last dose of study treatment.

The following contraception methods are not considered to be highly effective birth control methods and must not be used:

- Progestogen-only oral hormonal contraception, where inhibition of ovulation is not the primary mode of action
- Male or female condom with or without spermicide
- Cap, diaphragm or sponge with spermicide
- Combination of male condom with either cap, diaphragm or sponge with spermicide (double barrier methods).

Document No. CC	C O N F I D E N T I A L I N F O R M A T I O N	20/54
	Global Version ID: CCI	

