5.3 Selection of Study Population

Only participants that are ongoing with treatment in the Vertex study VX13-970-002 may be enrolled into this study. Participants will be transitioned from the VX13-970-002 study to enable them to continue treatment with berzosertib. Prior to performing any study assessments not part of the participant's routine medical care, the Investigator will ensure that the participant or the participant's legal representative has provided written informed consent following the procedure described in Section 9.2.

Document No. CCI	C O N F I D E N T I A L I N F O R M A T I O N	15/54	
	Global Version ID: CCI		

M6620

MS201923-0007

- Ongoing treatment in Vertex clinical study VX13-970-002 (parent study)
- Participant must be able to understand and provide written informed consent
- Participant must be willing and able to comply with the scheduled visits, treatment plan, lifestyle, laboratory tests, contraceptive guidelines (as described in Appendix I), and other study procedures.

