Appendix I: Contraception

Definitions:

Woman of Childbearing Potential (WOCBP)

A woman is considered fertile following menarche and until becoming postmenopausal unless permanently sterile, as specified below.

If fertility is unclear (e.g., amenorrhea in adolescents or athletes) and a menstrual cycle cannot be confirmed before the first dose of study intervention, consider additional evaluation.

A WOCBP is **not**:

- 1. Premenarchal
- 2. A premenopausal female with 1 of the following:
 - Documented hysterectomy
 - Documented bilateral salpingectomy
 - Documented bilateral oophorectomy

Documentation can come from the site personnel's review of the female's medical records, medical examination, or medical history interview.

For a female with permanent infertility due to an alternate medical cause other than the above, (e.g., Müllerian agenesis, androgen insensitivity), Investigator discretion applies to determine study entry.

- 3. A postmenopausal female
 - A postmenopausal state is defined as no menses for 12 months without an alternative medical cause.
 - A high FSH level in the postmenopausal range may be used to confirm a postmenopausal state in a female not using hormonal contraception or HRT. However, in the absence of 12 months of amenorrhea, more than 1 FSH measurement is required in the postmenopausal range.
 - A female on HRT and whose menopausal status is in doubt will be required to use one of • the nonestrogen hormonal highly effective contraception methods if she wishes to continue her HRT during the study. Otherwise, she must discontinue HRT to allow confirmation of postmenopausal status before study enrollment.

Contraception Guidance:

CONTRACEPTIVES ALLOWED DURING THE STUDY INCLUDE:

Highly Effective Methods That Have Low User Dependency

- Implantable progestogen-only hormone contraception associated with inhibition of ovulation
- Intrauterine device (IUD)
- Intrauterine hormone-releasing system (IUS)
- Bilateral tubal occlusion
- Vasectomized partner: a highly effective contraceptive method provided that the partner is the sole sexual partner of a WOCBP and the absence of sperm has been confirmed. Otherwise, use an additional highly effective method of contraception. The spermatogenesis cycle is approximately 90 days.

Highly Effective Methods That Are User Dependent

- Combined (estrogen- and progestogen-containing) hormonal contraception associated with inhibition of ovulation
 - Oral Intravaginal Transdermal Injectable

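### Do the two different contraception rules for women who stay on HRT (Protocol section 6.4.4.2 and Appendix I) call for a change to the plan?

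*Protocol*

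**What the plan says.** Two current parts of the protocol address a woman on HRT whose menopausal status is uncertain and who wants to stay on HRT.

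- Section 6.4.4.2, under women of nonchildbearing potential: a woman "whose menopausal status is in doubt will be required to use one of the non-hormonal highly effective contraception methods".
- Appendix I, in its definition of who is not of childbearing potential: she must use one of "the nonestrogen hormonal highly effective contraception methods if she wishes to continue her HRT during the study".

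Both give the same way out. In Appendix I it reads "Otherwise, she must discontinue HRT to allow confirmation of postmenopausal status before study enrollment", and section 6.4.4.2 says the same in nearly the same words.

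Both parts bind. The inclusion criterion requires a participant to be willing and able to follow the "contraceptive guidelines (as described in Appendix I), and other study procedures". Section 6.4.4.2 sends women of childbearing potential to the appendix: "A highly effective contraception as outlined in Appendix I must be used before start of first dose of study treatment". However, the same section opens by requiring contraception "as detailed below throughout the study and for 6 months after the last dose of assigned treatment" and then writes its own HRT rule. No order of precedence is given.

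**The concern.** The two sentences share the population, the trigger, the obligation and the alternative. They differ only in the class of method, and taken plainly the two classes exclude each other. A site that follows one sentence with one method has not followed the other. Using two methods, one of each class, would satisfy both, but neither section asks for two.

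Contraception is a participant safeguard, and section 6.4.4.2 extends it through the study and for 6 months after the last dose. It is therefore a continuing duty and not only an entry check. Under section 7.4.2 a participant's pregnancy means immediate discontinuation of study medication and expedited notification. If one of the two sentences gave weaker protection, the safeguard would depend on which page the site happened to read.

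**Working it through.** The documents state no figure to reproduce and no sample size calculation is involved. The check compares the texts and then counts who could be affected.

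**Step 1: sort the methods listed in Appendix I.** The list has 8 entries.

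| Class | Entries | Count |
|---|---|---|
| Non-hormonal | IUD; bilateral tubal occlusion; vasectomized partner; sexual abstinence | 4 |
| Hormonal, no estrogen stated | progestogen-only implant; hormone-releasing intrauterine system; progestogen-only oral or injectable | 3 |
| Estrogen-containing | combined hormonal methods | 1 |

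**Step 2: apply each sentence.**

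- Plain reading of the Appendix I phrase (hormonal, but without estrogen): 4 entries meet section 6.4.4.2, 3 meet Appendix I, and 0 meet both.
- Looser reading (anything that is not an estrogen hormone): 4 entries meet section 6.4.4.2, 4 + 3 = 7 meet Appendix I, and 4 meet both. The sections still differ on the 3 progestogen-only or hormone-releasing entries.

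So the texts differ on either reading, but the statement that no single method meets both holds only on the plain one.

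**Step 3: compare the protection required.** Both sentences call for a highly effective method. Section 6.4.4.2 and the notes to Appendix I define this identically, as a failure rate below 1% per year with consistent and correct use. A woman who will not use such a method must stop HRT under either text. The class of method changes; the required standard does not.

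**Step 4: count who could be affected.**

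- Current participants: Protocol section 3 reports one participant, from Part A1, still on treatment when VX13-970-002 was completed, and that participant transferred. Sex and HRT use are not stated. The number affected is 1 × (0 or 1) = 0 or 1. The pre-enrollment step of stopping HRT is already past for this person.
- New participants: section 5.3 limits entry to people with ongoing treatment in VX13-970-002. That study is complete, so the number is 0. Section 3.1 allows others only through an amendment.

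**Step 5: trace any effect on the analysis.** The primary endpoint is the occurrence of adverse events and treatment-related adverse events. The enrolled set depends on consent and the safety set on receiving a dose. SAP sections 7 and 9 restrict output to listings of data as collected. None of these uses the contraceptive method. Section 7.4.2 requires every pregnancy conceived in the reporting period to be recorded, whichever method was in use.

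**A neighbouring difference that does not add to the point.** Section 6.4.4.2 describes postmenopausal status as "age-related amenorrhea ≥ 12 consecutive months and increased follicle-stimulating hormone (FSH) > 40 mIU/mL", in a sentence whose subject is exemption from pregnancy testing, and then has FSH drawn only where needed. Appendix I uses 12 months without menses and lets FSH serve as confirmation. The wording is uneven, but the two can be read together.

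**The case for a change.** The strongest case for acting is that both sentences are mandatory, current and intact, and that they cannot both be met with one method on the plain reading. The cross-references do not settle it. The pointers from section 6.4.4.2 to Appendix I cover female partners and women of childbearing potential, whereas the HRT sentence sits under women of nonchildbearing potential. The protocol also foresees adding participants, sites and countries by amendment, and the same text would then be reused. Correcting it costs only wording.

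The inconsistency itself stands, and so does the point about reuse. What does not stand is the consequence. The claim that the safeguard depends on the page read would need one page to protect less than the other, and Step 3 shows the same standard in both. The open cross-references are also less open than they look, because the inclusion criterion names Appendix I alone. As for reuse, a new participant can enter only by amendment, so the occasion to reconcile the wording comes before anyone new could meet it.

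**Conclusion.** This is a clerical inconsistency, and changing it would gain nothing for the trial as it now stands. On the plain reading, 0 of 8 listed methods satisfy both sentences; on the looser reading, 4 do and the sections disagree on 3. The required standard of protection is the same in both texts. At most 1 current participant could be concerned, none is shown to be, and there are 0 possible new entrants under the current text. No endpoint, analysis set or planned data listing depends on the answer.

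This rests on two assumptions: that the participant described in section 3 is the only one enrolled, and that nobody else is added without an amendment. If participants are added, the two HRT sentences must be reconciled first. Which of them is clinically right is for the sponsor's medical team, and this review takes no position on it.

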6.4.5 Management of Specific Adverse Events or Adverse Drug Reactions

Based on the observations made so far, participants experienced significant physical discomfort, defined variably by diaphoresis, flushing, dyspnea, nausea, diarrhea, change in mental status, and/or hypotension several minutes after administration of their second dose of berzosertib. Investigators may prophylactically premedicate all participants with 200 mg hydrocortisone approximately 60 minutes before infusion, and 10 mg of chlorphenamine approximately 30 minutes before infusion.

6.5 Packaging and Labeling of the Study Intervention

Berzosertib will be packaged and labeled in accordance with all applicable regulatory requirements and Good Manufacturing Practice Guidelines.

6.6 Preparation, Handling, and Storage of the Study Intervention

Berzosertib single use vials must be carefully stored at CCI, in a location with restricted access, and separately from other drugs.

Following dilution of the test material, intravenous bags should be covered to protect from light and stored in the dark.

Any deviations from the recommended storage conditions should be immediately reported to the Sponsor, and the medication should not be used until authorization has been received from the Sponsor. The study interventions must not be used for any purpose other than the study. The administration of the study intervention to participants who have not been enrolled into the study is not covered by the study insurance.

Disposal of the study interventions should be according to local regulations and institutional guidelines.

6.7 Study Intervention Accountability

The Investigator is responsible for ensuring berzosertib accountability, including reconciliation of drugs and maintenance of records.

- Upon receipt of study intervention, the responsible person will check for accurate delivery and acknowledge receipt by signing or initialing and dating the appropriate documentation and returning it to the location specified. A copy will be archived for the Investigator Site File.
- Study intervention dispensing will be recorded on the appropriate drug accountability forms so that accurate records will be available for verification at each monitoring visit.
- Study site study intervention accountability records will include the following:
 - Confirmation of study intervention receipt, in good condition and in the defined temperature range

Document No. CCI	C O N F I D E N T I A L I N F O R M A T I O N	21/54	
	Global Version ID: CCI		

- > The inventory of study intervention provided for the clinical study and prepared at the site
- > The use of each dose by each participant
- > The disposition of any unused study intervention
- Dates, quantities, batch numbers, vial/kit numbers (as applicable), expiry dates, formulation (for study intervention prepared at the site), and the individual participant study numbers.

The Investigator site should maintain records, which adequately document that participants were provided the doses specified in this protocol, and all study interventions provided were fully reconciled.

Unused study intervention must not be discarded or used for any purpose other than the present study. No study intervention that is dispensed to a participant may be redispensed to a different participant.

A Study Monitor will periodically collect the study intervention accountability forms.

After completion of the study, any study intervention distributed to the site but not administered, dispensed to or taken by the participant(s) will be destroyed at the study site. Details will be agreed upon between the Sponsor and the Investigator. All unused medications will be carefully recorded and documented before destruction.

